## 1.4 SAMPLE SIZE

The sample size calculation is based on the primary endpoint which will be analysed on a  $\log_{10}$ -scale. The following assumptions are made:

- The combination intervention will confer a 50% reduction in total HIV DNA when compared with cART alone. On a  $\log_{10}$ -scale this corresponds to a difference between the two arms of  $\log_{10}(2)$  (approximately 0.3). The effect is assumed to be the same in both strata (recently and previously diagnosed patients).
- Standard deviation (SD) is 0.4 for a single measurement in both arms based on two publications:
  - Reported on data from 31 participants treated with HAART at PHI in the French PRIMO study. The median (IQR) at 6 and 12 months after starting treatment were 2.30 (2.10, 2.70) and 2.10 (1.80, 2.40)  $\log_{10}$  DNA copies/ $10^6$  PBMC respectively suggesting a SD of 0.45 at both time points.
  - Reported on 8 participants with PHI. At week 52, the median (IQR) was 494 (250 - 694) for total HIV-1 DNA copies/ $10^6$  CD4+ T-cells suggesting a SD (in log scale) of 0.33.
- 1:1 allocation of participants in the two study arms.
- Method of analysis: comparing the treatment arms in terms of absolute HIV total DNA level at post-randomisation weeks 16 and 18 adjusted for baseline (here: randomisation) level (analysis of covariance; ANCOVA); one baseline measurement and two follow-up measurements (at PR16 and 18) will be taken for an individual participant.
- A correlation coefficient of 0.5 between a baseline measurement and a PR 16/18 measurement, and a correlation coefficient of 0.7 for measurements at PR 16 and 18.
- Two-sided  $\alpha = 0.05$  for the null hypothesis that there is no difference between the two arms in the primary endpoint.

Under the above assumptions, a sample size of 52 individuals would provide 94% power to detect a 50% reduction in HIV total DNA (86% power for a 45% reduction).

Assuming that some individuals enrolled will not reach visits PR 16/18 (due to failing the eligibility criteria for randomisation in stratum I, or withdrawal) it is planned to enrol a total of 60 individuals overall (both strata combined).

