### 3 ANALYSIS PRINCIPLES

- The trial will be primarily analysed as intention-to-treat including all randomised participants. Based on the consideration that the trial is evaluating the efficacy, as measured by the impact on total CD4+ HV DNA of a novel intervention, sensitivity analyses will also be performed for immunological/virological outcomes excluding participants with incomplete intervention (temporary/complete stop of ART, vaccination, or vorinostat).
- Randomisation arms will be compared using data between baseline and the post-randomisation week 18 visit (inclusive). Data collected in the period between enrolment and randomisation will be reported for stratum I as baseline data.
- For continuous variables, the following will be presented by scheduled visits and by randomised group:
  - number of participants with a measurement
  - mean (SD) or median (IQR) of absolute values and of changes in absolute values from baseline
  - mean changes (plus point-wise 95% CI) from baseline in each randomised group, calculated using normal regression of absolute values, adjusting for the baseline measurement.
  - normal generalized linear regression models (using GEE) will be used for a global test of difference between treatment groups across all visits

If positively skewed, data will be log-transformed before the analysis. If parametric models/tests do not seem to be appropriate, rank tests will be performed.

- Binary and categorical variables will be tabulated, overall and by randomised group. Differences between groups at particular time-points will be tested using chi-squared tests (or exact tests if appropriate), and logistic regression models for adjusted analyses. GEE models will be used for a global test of difference between treatment groups across all visits.
- Time-to-event outcomes will consider time from baseline to the event date, using Kaplan-Meier estimation. For participants who have not reached the event in question, the date of last clinic visit will be used as a censoring time. Differences between groups in time-to-event outcomes will be tested using a log-rank test and Cox proportional hazard regression models (stratified by the stratification factors).
- Primary analyses will be adjusted for membership of stratum I versus stratum II; secondary analysis will be conducted without adjustment.

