- Multiple imputations will be performed to account for missing data in the primary outcome measure (see below). Analyses of secondary endpoint, unless otherwise stated, will be based on available data only. Reasons for missing efficacy data will be described.
- All estimates including differences between randomised groups will be presented with a 2-sided 95% confidence interval. All statistical tests will be 2-sided. P values will be given to 2 decimal places if  $\geq 0.10$ , otherwise to 1 significant figure.

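### The rank-test fallback for continuous outcomes should be a rank analysis of covariance, so that the planned baseline adjustment is kept

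*SAP*

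**What the plan says.** SAP section 3 sets a general method for continuous variables: summaries by visit, mean changes from a normal regression adjusted for the baseline measurement, and a GEE model for a global test across visits. Positively skewed data are log-transformed first. The fallback is one sentence: "If parametric models/tests do not seem to be appropriate, rank tests will be performed". The test, the trigger and the handling of covariates are not given.

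The outcomes that refer back to this rule are integrated HIV DNA, T cell responses, viral inhibition and inflammatory biomarkers (SAP section 4.7), and CD4 count, CD4:CD8 ratio and the quality-of-life score (section 4.9). For integrated DNA, section 4.7 also requires adjustment for the baseline level and stratum.

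The primary endpoint has a separate rule. SAP section 4.6 fixes an analysis of covariance (ANCOVA) on the log10 scale, adjusted for baseline and stratum, and lists no rank fallback. Protocol section 9.5 agrees.

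The planning values in SAP section 1.4 take an SD of 0.4 for one measurement. For the link from baseline to follow-up they assume "A correlation coefficient of 0.5 between a baseline measurement and a PR 16/18 measurement". The two follow-up visits are taken to correlate at 0.7.

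**The concern.** A two-sample rank test of follow-up values uses neither baseline nor stratum. If the fallback is applied in that form, an outcome planned with baseline adjustment is tested without it, and for integrated DNA two SAP instructions cannot both be followed.

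The wording elsewhere favours the ordinary, unadjusted meaning. For cell-associated RNA, section 4.7 offers paired rank tests as the counterpart of paired t-tests. Where the SAP wants an adjusted method that tolerates awkward distributions, it says so: viral outgrowth is given median regression with stratum and baseline adjustment. For binary outcomes, section 3 names logistic regression for the adjusted analysis. The continuous fallback has no such companion.

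What is at stake is power on the outcomes most likely to trigger the fallback, when a rank method that keeps the covariates is readily available.

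**Working it through.** No secondary outcome has its own planning values, so those of the primary endpoint serve as an illustration.

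**Inputs (SAP section 1.4).** 26 per arm (52 at 1:1); two-sided alpha 0.05; single-measurement SD 0.4; correlation 0.5 baseline to follow-up and 0.7 between weeks 16 and 18; effect log10(2) = 0.3010 for a 50% reduction and -log10(0.55) = 0.2596 for 45%.

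**Step 1: reproduce the plan's power.**
- Variance of the mean of two follow-ups: 0.16 × (1 + 0.7)/2 = 0.136.
- Residual variance after baseline: 0.136 - 0.5² × 0.16 = 0.096, SD 0.310.
- Standard error of the difference: 0.310 × √(2/26) = 0.0859.
- 50%: 0.3010/0.0859 - 1.96 = 1.54, power 93.9% (SAP: 94%).
- 45%: 0.2596/0.0859 - 1.96 = 1.06, power 85.6% (SAP: 86%).

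**Step 2: unadjusted rank test, normal data.**
- SD without baseline: √0.136 = 0.369.
- Effective number per arm at relative efficiency 3/π: 26 × 0.955 = 24.8.
- Power 82.0% at 50% and 69.9% at 45%. Simulation gave 80% and 69%.
- Most of the loss comes from dropping baseline: an unadjusted comparison of means already has only 83.7%.

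**Step 3: compare the rank methods by simulation.** Quade's method ranks the outcome and the baseline over both arms, regresses one on the other (with stratum where wanted), and compares the residuals between arms. Power at a 50% reduction, n = 52; the non-normal shapes are assumptions:

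| Data | ANCOVA | Unadjusted rank | Rank ANCOVA | Rank ANCOVA minus unadjusted rank |
|---|---|---|---|---|
| Normal | 93% | 80% | 91% | 11 |
| Assay floor (0.75 SD below control mean; lower values set to half the floor) | 89% | 77% | 88% | 11 |
| Strong left skew (reversed exponential) | 91% | 95% | 99% | 4 |
| Milder left skew (sums of reversed exponentials) | 93% | 88% | 95% | 7 |
| Heavy tails (t, 3 df) | 94% | 96% | 99% | 3 |

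At a 45% reduction, ANCOVA / unadjusted rank / rank ANCOVA gave 83/68/80 (normal), 80/66/78 (floor), 84/78/88 (milder skew) and 88/91/96 (heavy tails).

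Type I error of the rank ANCOVA ranged from 4.3% to 5.9%. With 4,000 to 5,000 trials, the Monte Carlo standard error near 80% power is about √(0.8 × 0.2/4000) = 0.6 points.

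**Step 4: rank test on change from baseline.** Its variance is 0.136 + 0.16 - 2 × 0.5 × 0.16 = 0.136, the same as for follow-up alone, so at correlation 0.5 it recovers nothing (about 80% in simulation).

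**The case against.** Several points on the other side stand and limit the finding.

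- **The SAP does not say that adjustment is dropped.** A rank ANCOVA would fit the same words. The sentence permits an unadjusted test, and its ordinary reading is one, but it does not prescribe it.
- **The 94% belongs to the primary endpoint.** A reader might infer that the trial's main power would fall from 94% to about 80%. The documents do not support that: section 4.6 fixes ANCOVA for total DNA and gives no fallback. Section 3 does not expressly exempt the primary endpoint, so the reach is unclear rather than established. No secondary outcome has a stated power to lose.
- **A loss of over 10 points against ANCOVA is not general.** It appears with normal data, where the fallback should not be triggered, and with floored data. With heavy tails or strong skew the unadjusted rank test beats ANCOVA. The decision at issue, however, is which rank method to use once the fallback is triggered, and there the rank ANCOVA was better in every setting.
- **A rank test on change does use baseline.** At correlations of 0.7 and 0.8 the change has variance 0.16 × 0.9 + 0.16 - 2 × 0.7 × 0.16 = 0.08 (SD 0.283) and about 96% power. A contrast there of 98% for ANCOVA against 78% for follow-up values alone would therefore mislead.
- **Some floor problems are already handled.** Viral outgrowth has its own censored and median-regression plan, and ultra-low-copy RNA is analysed as binary.
- **Stratum.** Section 3 plans secondary analyses without stratum adjustment, so where that applies no planned stratum adjustment is lost.
- **Quade's test gives no estimate on the original scale**, whereas section 3 asks for estimates with 95% confidence intervals. Nor does it replace the GEE global test.

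**Conclusion.** The point holds as a defect in one sentence of SAP section 3, mainly for the secondary and other outcomes that inherit it. In its ordinary reading the fallback gives up the baseline adjustment, and for integrated DNA it conflicts with section 4.7. Under the planning values and a 50% reduction, keeping the covariates is worth about 11 points of power with normal or floored data and about 3 to 7 points with the skewed or heavy-tailed shapes tried.

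These sizes rest on borrowing the primary endpoint's SD and correlations for other outcomes, and on assumed non-normal shapes. They show which rank method is better; they do not forecast the power of any named secondary outcome, and they do not show that the primary analysis is underpowered.

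**What to change.** Replace the sentence in SAP section 3 with wording such as: *rank-based analysis of covariance (Quade), adjusting for the baseline value, and for stratum where the planned analysis adjusts for it, will be performed.* State in the same place that this fallback does not replace the primary ANCOVA in section 4.6. An unadjusted rank test can stay as a secondary check.

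Because the rank method yields no effect size on the original scale, keep reporting the adjusted regression estimate with its 95% confidence interval beside the rank p-value. State also that the method applies to comparisons at a visit and does not stand in for the GEE test across visits.

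The cost is a short SAP amendment, a few lines of code, and about 2 to 3 points of power relative to ordinary ANCOVA if the data are in fact normal.

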#### **9.5 ANALYSIS PLAN (BRIEF)**

The analyses will be described in detail in a full Statistical Analysis Plan. This section summarises the main issues.

HIV total DNA from CD4 T-cells average at post-randomisation weeks 16 and 18 (PR16 and PR18) will be compared between the two groups as allocated (intention to treat, ITT) by analysis of covariance with adjustment for values at randomisation. The analysis will be performed on all eligible participants randomised taking into account stratification factors. An imputation method will be used to estimate missing HIV total DNA values in participants with unobserved values and this will be defined in the Statistical Analysis Plan.

The frequency of grade 3 and 4 adverse events will be tabulated by body systems and randomised group and the groups will be compared using Fisher's exact test.

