## 4.7 SECONDARY ENDPOINTS: EFFICACY

- HIV integrated DNA:**

Measurements (copies/million CD4+T cells) at enrolment (in recently infected patients), baseline, PR week 08-3, PR week 12-2, PR week 16, and PR week 18.

Analysed as for continuous outcomes as specified above. Treatment arms will be compared in terms of absolute integrated HIV DNA levels at post-randomisation weeks 16 and 18 adjusted for the baseline level and by stratum.

- Plasma HIV RNA measured with an ultra-low copy assay:**

Number (%) with undetectable HIV-RNA at enrolment (in recently infected patients), baseline, PR week 08-3, PR week 09-2, PR week 12-2, PR week 16, and PR week 18; analysed as for binary outcomes as specified above.

- **Replication competence (Viral Outgrowth assay):**

Measurements (infectious units per million cells; IUPM) at baseline and PR week 16. Analysed as for binary and continuous outcomes as specified above. The results are expected to be “negative” (i.e. below the lower limit of detection) in a sizable proportion of samples. Therefore, the treatment arms will be compared as follows:

- 1) Primary analysis:
  - a) Comparison of the proportion of patients with a “negative” result using logistic regression. This analysis includes all patients with a valid PR-16 result.
  - b) Comparison of IUPM in patients with “positive” results using median regression. Patients with a “negative” PR-16 result will be excluded.
- 2) Secondary analysis:  
Comparison of IUPM using a linear model appropriate for left-censored data. This analysis includes all patients with a valid PR-16 result, “positive” or “negative”.

In all analyses, patients with missing PR-16 samples or invalid PR-16 results (due to assay failure) will be ignored. Analyses will be adjusted for stratum and baseline viral outgrowth. Missing baseline values will be imputed; predictors may include stratum, and other factors associated eg CD4, HIV-DNA.

- **HIV-specific T cell responses (both CD8+ and CD4+ T cell responses):**

Measurements using intracellular cytokine staining (ICS) at enrolment (in recently infected patients), baseline, PR week 09-2, PR week 12-2, and PR week 16. For both CD8+ and CD4+ T cells, the following markers will be measured: CD107a+, CD154+, IFNg+, IL2+, and TNFa+.

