For each marker, the magnitude of a response is defined as the number of positive cells as percentage of their parental populations, after subtracting the negative control. For technical reasons, HIV antigens will be divided in non-overlapping pools values for each sample; responses will be added up for each marker.

At each time-point, the magnitude of responses, and the change from baseline will be analysed as for continuous outcomes as specified above.

- **CD8+ T cell antiviral activity (viral inhibition)**

Measurements using a flow cytometer-based assay [2] at enrolment (in recently infected patients), baseline, PR week 09-2, PR week 12-2, and PR week 16.

CD8+ T cell antiviral suppressive activity will be expressed as percentage inhibition and determined as follows:  $\frac{[(\text{fraction of p24} + \text{cells in CD4} + \text{T cells cultured alone}) - (\text{fraction of p24} + \text{in CD4+ T cells cultured with CD8+ cells})]}{(\text{fraction of p24} + \text{cells in CD4} + \text{T cells cultured alone})} \times 100$ .

CD8+ T cell antiviral suppressive activity will be analysed as described above for continuous outcomes.

- **Inflammatory biomarkers:**

For example CD4:8 ratio, immune exhaustion/activation markers, IL-6 and d-dimer, neuro-inflammation markers. Analysed as for continuous outcomes as specified above.

- **HIV cell associated RNA (arm B only):**

Measurements (copies/million 18S copies) pre and 2 hours post vorinostat at visits PR week 08-3, PR week 09-2, and PR week 12-2. Comparison of pre and post vorinostat values will be performed using paired t-tests (or paired rank-tests if appropriate).

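### SAP 3 does not make clear whether secondary efficacy endpoints are adjusted for the randomisation stratum, and four of the six between-arm endpoints rest on templates with no stratum term

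*SAP*

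**What the plan says.** Randomisation is stratified by Cohort I and Cohort II (Protocol 9.1; SAP 1.1, where they are called strata). SAP 3 then states: "Primary analyses will be adjusted for membership of stratum I versus stratum II; secondary analysis will be conducted without adjustment".

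The templates in the same section are:

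- **Continuous outcomes:** normal regression with the baseline value as the only named covariate, a GEE model for a global test across visits, and rank tests if parametric methods look unsuitable. No stratum term is named.
- **Binary outcomes:** chi-squared or exact tests at each visit, logistic regression for adjusted analyses (covariates not named), and GEE across visits.
- **Time-to-event outcomes:** a log-rank test with no mention of stratum, and a Cox model that is stratified.

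SAP 4.7 names stratum for two secondary endpoints. Integrated HIV DNA is adjusted for baseline and stratum. For viral outgrowth, "Analyses will be adjusted for stratum and baseline viral outgrowth". The other between-arm endpoints refer back to the templates: ultra-low-copy RNA is "analysed as for binary outcomes as specified above", and for viral inhibition "CD8+ T cell antiviral suppressive activity will be analysed as described above for continuous outcomes". T cell responses and inflammatory biomarkers are handled in the same way. Cell-associated RNA is a paired comparison within arm B, so the question does not arise there.

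**The concern.** When randomisation is stratified, the arms are balanced on the stratum by design. An analysis that leaves the stratum out keeps the between-stratum variance in its error term, although that variance no longer contributes to the arm difference. Standard errors are then too large, the test runs below its nominal level and power falls. All of this depends on the stratum being prognostic after any baseline adjustment.

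It could be. Protocol 3.3.3 expects most Cohort I participants to be randomised around week 23 of ART, while Protocol 5.2.3 admits Cohort II with between 22 weeks and 2 years of ART. With about 52 analysable participants, precision is scarce. T cell responses and viral inhibition bear on the proposed mechanism (Protocol 1.3), so they would matter for interpreting a null primary result.

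There is also a question of pre-specification. For ultra-low-copy RNA the binary template offers both a chi-squared test and a logistic model without saying which is the main result. In an open-label trial that should be settled beforehand.

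**Working it through.** **1. The plan's own figure.** SAP 1.4 sets "Two-sided $\alpha = 0.05$ for the null hypothesis" and assumes: "The combination intervention will confer a 50% reduction in total HIV DNA when compared with cART alone". It gives an SD of 0.4, a baseline to follow-up correlation of 0.5 and a correlation of 0.7 between the two follow-up visits. It concludes that "a sample size of 52 individuals would provide 94% power to detect a 50% reduction in HIV total DNA", and 86% for a 45% reduction.

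- ANCOVA variance for the mean of two follow-ups: 0.4² × [(1 + 0.7)/2 − 0.5²] = 0.16 × 0.60 = 0.096, so SD = 0.3098.
- Standard error with 26 per arm: 0.3098 × √(2/26) = 0.0859.
- 50% reduction: Φ(0.3010/0.0859 − 1.96) = 93.9%.
- 45% reduction: Φ(0.2596/0.0859 − 1.96) = 85.6%.

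Both stated figures reproduce. The primary analysis is adjusted for stratum (SAP 4.6), so this point does not touch it.

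**2. Continuous secondary endpoints.** The documents give neither the stratum sizes nor a stratum effect. Assume a stratum shift of g residual SDs remaining after baseline adjustment, a share q in one stratum, and arms balanced within stratum. Omitting stratum inflates the error variance by 1 + g²q(1 − q), and the approximate test level is 2Φ(−1.96 × √[1 + g²q(1 − q)]). For g = 1 and q = 0.5 the inflation is 1.25 and the level is 2Φ(−2.19) = 0.028.

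Simulation with 20,000 runs, N = 52, a 26/26 split and an effect sized for 80% power by the normal approximation gives:

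| g | Variance inflation | Level, omitted v included | Power, omitted v included |
|---|---|---|---|
| 0.25 | 1.016 | 0.047 v 0.048 | 78.1% v 78.6% |
| 0.5 | 1.062 | 0.043 v 0.049 | 77.2% v 78.9% |
| 1.0 | 1.25 | 0.030 v 0.051 | 70.9% v 78.4% |
| 1.5 | 1.562 | 0.013 v 0.050 | 61.0% v 78.2% |

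The included column sits a little under 80% because the tests use the t distribution. Unequal strata reduce the loss: with a 40/12 split and g = 1.0 the level is 0.033 v 0.051 and power is 72.9% v 78.5%.

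**3. Binary secondary endpoint.** Assume 13 per arm per stratum and a treatment odds ratio of 5. Compare the plain chi-squared test with Cochran-Mantel-Haenszel (no continuity correction, 20,000 runs):

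| Control rates by stratum | Level, chi-squared v CMH | Power, chi-squared v CMH |
|---|---|---|
| 40% v 60% | 0.044 v 0.052 | 74.2% v 74.0% |
| 30% v 70% | 0.029 v 0.053 | 66.8% v 70.0% |
| 20% v 80% | 0.011 v 0.050 | 49.6% v 62.0% |

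The stratum odds ratios implied are (0.6/0.4)² = 2.25, (0.7/0.3)² = 5.4 and (0.8/0.2)² = 16.

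**The case against.** A reader might infer that SAP 3 rules out stratum adjustment for every secondary endpoint. The documents do not support that. The sentence sets primary analyses against secondary analysis, not against secondary endpoints. Where SAP 3 means endpoints, as in its missing-data bullet, it says so. SAP 4.7 labels a primary and a secondary analysis within viral outgrowth, which is itself a secondary endpoint. Read this way, the sentence is a general principle that supplies the stratum term the templates omit, and it agrees with SAP 4.7 and with the stratified Cox model. This reading is at least as coherent as the other. What it leaves open is that the chi-squared, exact and rank tests named in SAP 3 cannot carry a stratum term, and no stratified versions are given.

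A reader might also infer that the loss is certain, or that false positives increase. Neither follows. Protocol 1.3 argues that total HIV DNA plateaus and that the cohorts will be comparable. The permitted ART durations overlap, and both cohorts must have undetectable HIV RNA at randomisation. These arguments stand for reservoir DNA. The plateau argument does not address T cell function or inflammatory markers. The wider binary contrasts above are large assumptions with no support in the documents.

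The limits of the point should also be clear. The phrase "taking into account stratification factors" in Protocol 9.5 concerns the primary endpoint, so it shows no departure for secondary ones. CD4 count and quality of life are classed under other endpoints (SAP 4.9). No efficacy endpoint in SAP 4.6 or 4.7 is described as time-to-event, so the unstratified log-rank test is of no consequence here. Protocol 9.5 names Fisher's exact test for grade 3 and 4 adverse events, and a blanket rule to adjust every secondary comparison would contradict it.

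**Conclusion.** The point holds as an ambiguity and an omission. SAP 3 can be read in two ways, one of which conflicts with SAP 4.7. On either reading, ultra-low-copy RNA, T cell responses, viral inhibition and inflammatory biomarkers are sent to templates that do not name the factor used in randomisation.

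The consequence runs in the conservative direction only and is conditional on the stratum being prognostic beyond baseline. For continuous outcomes the cost is negligible to small up to a 0.5 SD residual shift (1.7 points at 0.5 SD) and becomes material at 1 SD (7.5 points with equal strata, 5.6 with a 40/12 split). For a binary outcome it is nil at 40% v 60% and about 3 points at 30% v 70%. These stratum effects and stratum sizes are assumptions. The primary endpoint and its stated power are unaffected.

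This is a low-severity correction, worth making because it costs nothing and fixes the main analysis in advance.

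**What to change.** Replace the sentence in SAP 3 with: *The main analysis of every between-arm comparison of primary and secondary efficacy endpoints is adjusted for stratum; unadjusted analyses are supportive.*

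Then align the templates:

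- Add stratum to the continuous regression and to the GEE models.
- For binary efficacy outcomes, make logistic regression with stratum the main analysis, or Cochran-Mantel-Haenszel or a stratified exact test where data are sparse.
- Where rank methods are used, specify a stratified rank test (van Elteren).
- Leave the Fisher's exact comparison of grade 3 and 4 adverse events in Protocol 9.5 unchanged.

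The cost is SAP wording and one covariate that is already recorded for every randomised participant. No new data are needed, and the sample size does not change.

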## 2 DEFINITIONS

### 2.1 DEFINITION OF BASELINE

Baseline is defined in this trial as the time of randomisation. Baseline values used to define changes in immunological, virological and other measurements over time for each participant are defined as the measurements at randomisation. If a measurement at randomisation is not available, then the measurement at week 22 (stratum I) or screening (stratum II) closest to randomisation (but within 14 days before) will be used. If no measurement is available at or prior to randomisation then any measurement taken up to 7 days post-randomisation will be used providing this is before the start of vaccination.

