### **Handling of missing total HIV DNA measurements**

If either the PR week 16 result or the PR week 18 result is entirely missing but not both, the primary endpoint consists of the single available result. If total HIV DNA is missing at both PR-16 or PR-18, or at baseline, an imputation method will be used to estimate missing values. Predictors may include stratum, total HIV DNA from previous time-points and other factors associated with total HIV DNA eg CD4.

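### For integrated HIV DNA, HIV-specific T cell responses and CD8+ viral inhibition, a missing randomisation sample removes a participant whose outcome was measured, although the SAP imputes a missing baseline for total HIV DNA and viral outgrowth

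*SAP*

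**What the plan says.** SAP section 3 plans multiple imputation for missing values of the primary outcome and then sets the default for the rest: "Analyses of secondary endpoint, unless otherwise stated, will be based on available data only".

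The same section gives the general method for continuous outcomes. Mean changes are "calculated using normal regression of absolute values, adjusting for the baseline measurement". SAP 4.7 repeats the adjustment for integrated HIV DNA: "Treatment arms will be compared in terms of absolute integrated HIV DNA levels at post-randomisation weeks 16 and 18 adjusted for the baseline level". Stratum is a further adjustment term there. HIV-specific T cell responses, viral inhibition and inflammatory biomarkers are referred to the general method for continuous outcomes.

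Two endpoints have their own rule for a missing baseline. For the primary endpoint (SAP 4.6): "If total HIV DNA is missing at both PR-16 or PR-18, or at baseline, an imputation method will be used to estimate missing values". For viral outgrowth, a secondary endpoint (SAP 4.7): "Missing baseline values will be imputed; predictors may include stratum" and related factors. Participants with a missing or invalid PR16 outgrowth result are left out.

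SAP 2.1 also has a fallback for all measures. If there is no value at randomisation, "then the measurement at week 22 (stratum I) or screening (stratum II) closest to randomisation (but within 14 days before) will be used". Failing that, a value from the first 7 days after randomisation may serve if it precedes vaccination.

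**The concern.** A regression that adjusts for baseline needs a baseline value for everyone in it. If only available data are used, a participant without that value leaves the model even when PR16 or PR18 was measured.

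Total and integrated HIV DNA share one sample row in the protocol's Table 1. If the randomisation tube is lost, the participant stays in the primary analysis through imputation but leaves the integrated DNA comparison. The two reservoir measures would then be compared on different sets of people. In a trial sized on 52 evaluable participants, each such loss also costs some precision, for a reason that has nothing to do with the outcome.

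**Working it through.** **Does the SAP 2.1 fallback help?** The column totals in the protocol's Table 1 (Cohort I) show which tubes are drawn at each visit:

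- Enrolment: 80 (reservoir) + 32 (immunology) = 112 ml, the stated total.
- Week 22: 34 ml in total, all of it routine blood.
- Randomisation: 27 (routine) + 80 (reservoir) + 250 (outgrowth) + 32 (immunology) = 389 ml, the stated total.
- PR00: 0 ml.

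So neither step of the fallback has a scheduled Cohort I sample for integrated DNA, T cell responses or viral inhibition. The enrolment sample is taken at week 0, far outside the 14-day window. CD4 and CD8 counts are drawn at week 22, so the fallback can work for them. Table 2 (Cohort II) is not in the text available to this review.

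**Inputs.** From SAP 1.4: SD 0.4 on the log10 scale, correlation 0.5 between baseline and follow-up, correlation 0.7 between PR16 and PR18, n = 52, 1:1 allocation, two-sided 5%. These are the primary endpoint's values, borrowed here for integrated DNA. The missing fraction f is assumed.

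**Reproducing the plan's power.**

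- Variance of the PR16/PR18 mean: 0.16 × (1 + 0.7)/2 = 0.136.
- Part explained by baseline: 0.16 × 0.5² = 0.040.
- Residual variance: 0.136 − 0.040 = 0.096.
- Normal approximation, 26 per arm: 93.9% power for a 50% reduction (0.301 log10) and 85.6% for a 45% reduction (0.260 log10). The SAP states 94% and 86%.

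The sample size calculation is therefore not in question. The noncentral t distribution, used below, gives 93.0% and 84.1% with no baseline missing (48 df).

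**Dropped against kept.**

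- Dropped: 52(1 − f) participants, residual variance 0.096.
- Kept: 52 participants in an ordinary regression. The filled-in baseline is treated as carrying no information, so the average residual variance is (1 − f) × 0.096 + f × 0.136 = 0.096 + 0.040f.
- Information ratio, kept to dropped: 0.096 / [(0.096 + 0.040f)(1 − f)].
- Degrees of freedom: number analysed minus 4 (intercept, arm, baseline, stratum).

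| Assumed missing | Information ratio | Power, 50% reduction: dropped / kept | Power, 45% reduction: dropped / kept |
|---|---|---|---|
| 5% | 0.096/(0.098 × 0.95) = 1.03 | 91.6% / 92.5% | 82.2% / 83.4% |
| 10% | 0.096/(0.100 × 0.90) = 1.07 | 90.1% / 92.0% | 80.0% / 82.7% |
| 20% | 0.096/(0.104 × 0.80) = 1.15 | 86.3% / 90.9% | 74.9% / 81.2% |

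The confidence interval is wider by the square root of the ratio when these participants are dropped: about 1.5%, 3% and 7%.

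**Check for bias.** In a simulation (4,000 runs per setting, baselines missing at random, overall-mean substitution), 10 of 52 missing and a true difference of −0.301 gave mean estimates of −0.301 dropped and −0.300 kept. Power was 85.9% dropped and 90.5% kept, in line with the 20% row.

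**The case against.** Four arguments on the other side carry weight.

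- The SAP nowhere says that a participant without a baseline is excluded. That is inferred from combining two rules. The SAP also does not say whether the GEE global test conditions on baseline, so such a participant might still contribute there. This stands, but an available-data regression with a baseline covariate has no other default.
- The size has no anchor in the documents. No rate of missing baselines is given, the sample is scheduled at the randomisation visit itself, and no power is claimed for any secondary endpoint. This stands: 20% is hypothetical, and if few samples fail, little is lost.
- Using available data for secondary endpoints is a legitimate choice, and the SAP will report the number measured and the reasons for missing efficacy data. This stands too, but the SAP gives no reason for treating integrated DNA differently from total DNA or outgrowth.
- The Cohort II schedule was not available, so the failure of the fallback is shown for Cohort I only.

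A reader might infer three stronger points that the documents do not support.

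- *Every baseline-adjusted secondary comparison is affected.* It is not. Viral outgrowth has its own imputation rule, CD4 and the CD4:CD8 ratio have a week 22 value in Cohort I, and cell-associated RNA is a within-visit comparison in arm B. Unadjusted tests of ultra-low-copy RNA need no baseline.
- *The treatment comparison is biased.* With loss unrelated to arm, both approaches were unbiased in the simulation.
- *The intention-to-treat principle is broken.* SAP section 3 applies that principle primarily and openly sets a different rule for secondary endpoints. The fix below would not restore all randomised participants either, because missing outcomes stay missing.

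**Conclusion.** The point holds for integrated HIV DNA, HIV-specific T cell responses and CD8+ viral inhibition, and for any biomarker sampled only at randomisation. The SAP's rules, read together, set aside measured outcomes for want of a baseline, while for total HIV DNA and viral outgrowth the SAP imputes it.

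The consequence is a modest loss of precision and different participants behind two closely related reservoir measures. At an assumed 5% to 20% missing, the loss of power is about 1 to 5 percentage points for a 50% reduction and 1 to 6 for a 45% reduction. This rests on the primary endpoint's SD and correlations applying to integrated DNA, on 52 participants with a measured outcome, and on loss unrelated to arm. The T cell and inhibition endpoints have no SD or correlation in the documents, so no figure is claimed for them. This is an inexpensive improvement, not a threat to the trial's conclusions.

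**What to change.** Add to SAP section 3:

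> For baseline-adjusted secondary analyses, after applying section 2.1, participants with a measured outcome and a missing baseline are kept; the missing baseline is replaced by its predicted value from stratum (and the enrolment value in stratum I), without using arm. Missing outcomes stay unimputed.

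This follows the pattern the SAP already uses for viral outgrowth, where the baseline is filled in and a missing PR16 result is not. Settling it in advance also avoids choosing a rule after the data have been seen.

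The cost is a sentence or two of SAP wording and a few lines of code, with no extra samples or visits. The downside is that the adjustment is weaker for participants whose baseline is predicted; the calculation above already allows for this by giving the predicted value no credit.
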